## Responder Analysis

### Subject responders

The responder analyses at Week 48, Week 72 and Week 96 will be based on a randomization test comparing the observed rate of responders to the expected rate of responders under  $H_0$  (i.e. absence of treatment effect). Expected rate is defined as responder rate in the Sham group based on an improvement of at least 15 letters in the ETDRS score compared to baseline or being greater than a Snellen acuity equivalent of 20/200.

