## 3.3 SAMPLE SIZE CONSIDERATIONS

Sample size calculation is based on the primary endpoint (LogMAR) and on the paired comparison of treated and sham eye. There is no published data regarding the within subject variance and the sample size calculation through paired comparison will therefore be very speculative for two reasons. The first reason is the within subject correlation between right and left eye and the second reason is the absence of information on the within and between subject variance of the LogMAR. Usually the within subject correlation is positive and the use of a null correlation is conservative. The absence of information on the LogMAR requires a second rough

approximation of the mean and variance of LogMAR because the mean of ETDRS (Lam et al. 2014) is highly correlated to the variance of ETDRS ( $R^2 = 0.839$  for the log-log relationship). This correlation is in favor of the use of the LogMAR to stabilize the variance but the transformation from ETDRS mean and variance to LogMAR mean and variance requires additional assumptions. Starting with a mean 23.4 and a standard deviation of 28.3 (Lam et al. 2014) and a difference of 20 letters on average between treated and sham eye, using the relationship between the log mean and the log variance obtained with Lam et al. (2014) results (log variance =  $1.743 \log \text{mean} + 0.48$ ,  $R^2 = 0.839$ ) and assuming a perfect lognormal distribution of ETDRS, the difference in means of the lognormal distributions is 0.65 (3.32 - 2.67) and the pooled standard deviation of the log distributions is 0.914. Assuming no correlation between both eyes, the within subject standard deviation is  $(2 \times 0.914^2)^{0.5} = 1.29$ . The standardized difference in means is therefore  $0.65/1.29 = 0.504$  rounded to 0.50. The sample size required to get a power of 85% is exactly 36 subjects.

In GS-LHON-CLIN-01(Phase I/II study), at Week 48 the standard deviation (SD) for visual acuity of the between-eye difference in change from baseline was calculated as 0.594. Considering that in Phase III studies of GS010 detection of a 15 ETDRS letters or 0.3 LogMAR difference between treated and untreated eyes at outcome is a clinically reliable difference, the SD of the difference of 0.594 would provide a power/probability of 84% to detect such a difference based on the enrolment goal of 36 subjects each in the RESCUE and REVERSE Phase III clinical trials.

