### 3.4 RANDOMIZATION

The right eye of each subject will be randomly allocated to receive either GS010 or sham treatment in a 1:1 allocation ratio. The fellow (left) eye will receive the treatment not allocated to the right eye. Therefore, each subject will receive GS010 in one eye and sham treatment in the fellow eye. Prior to randomization, each subject's best- and worst-seeing eye will be determined. Efron's minimization method will be used in the randomization process to balance as much as possible the two treatment groups (GS010 and sham) in the best-seeing eyes.

To enroll a subject (Visit 1), the Investigator will call an interactive response system (IRS) and provide brief details about the subject to be enrolled. Each subject will receive a subject number assigned at screening, which will serve as the subject identifier throughout the study. The subject number will be required in all communication between the Investigator (or designee) and the IRS regarding a particular subject. Subject numbers will be tracked via the IRS.

To randomize a subject (Visit 2), the Pharmacist (or designee) will call the IRS and provide brief details about the subject to be randomized. Eligible subjects will be randomized in a 1:1 ratio (right/left eye), taking into account the Efron's minimization method, using the IRS.

The IRS User Guide will describe the steps of the randomization process from the subject's screening up to before IVT injection.

An algorithm with a testing hierarchy will be employed prior to randomization to determine the best- and worst-seeing eye of each subject, as follows:

1. ETDRS visual acuity score for subjects able to read the ETDRS chart. The eye with the higher ETDRS score is the best-seeing eye. For subjects who cannot read the ETDRS chart (“off chart” subjects) a standard study procedure will be used to determine visual acuity based on counting fingers at a given distance. The eye with the best visual acuity based on this method is the best-seeing eye. If one eye of a subject is able to read letters on the ETDRS chart and one eye cannot, the eye able to read the ETDRS chart is the best-seeing eye.
2. SD-OCT parameters (to be used if there is no inter-eye difference based on Criterion 1):

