### Responder

#### Eye Responder

##### Definition 1

Responder will be defined as an improvement of at least 15 letters in the ETDRS score compared to baseline, *or* being better than a Snellen acuity equivalent of 20/200. Early discontinuations will be considered as a non responder. For Week 96, two analyses will be performed: one for completers and one for subjects who don't have the Week 96 value available. If the Week 96 ETDRS score is not available, then the previous visit value will be used.

##### Definition 2

Responder will be defined by having an ETDRS Score equal to or greater than 20 letters. Early discontinuations will be considered as a non responder. For Week 96 two analyses will be performed: one for completers and one for subjects who don't have the Week 96 value available. If the Week 96 visual acuity score is not available, then the previous visit value will be used.

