## Subject Responder

Responder will be defined as a subject whose ETDRS score of the treated eye is at least 15 letters better than the sham eye *or* whose treated eye has a LogMAR acuity of at least 0.3 LogMAR better than the sham eye. Early discontinuations will be considered as non responder. For Week 96, two analyses will be performed: one for completers and one for subjects who don't have the Week 96 value available. If the Week 96 visual acuity score is not available, then the previous visit value will be used.

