## Subject Responder

### Criteria 1

Responder will be defined as a subject whose change of LogMAR from baseline in the treated eye is at least -0.2 better than the change from baseline of LogMAR in Sham eye. Early discontinuations will be considered as non-responders.

### Criteria 2

Responder will be defined as a subject whose change of LogMAR from baseline in the treated eye is at least -0.3 better than the change from baseline of LogMAR in Sham eye. Early discontinuations will be considered as non-responders.

### Criteria 3

Responder will be defined as a subject whose change of LogCS from baseline in the treated eye is at least +0.2 LogCS better than the change from baseline of LogCS in Sham eye. Early discontinuations (prior to W48 for the primary endpoint) will be considered as non-responders.

### Criteria 4

Responder will be defined as a subject whose change of LogCS from baseline in the treated eye is at least +0.3 LogCS better than the change from baseline of LogCS in Sham eye. Early discontinuations (prior to W48 for the primary endpoint) will be considered as non-responders.

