## ETDRS/LogMAR and on-chart and off-chart:

- I. 1 ETDRS line = 5 letters
- II. 1 ETDRS line = 0.1 LogMAR
- III. 0.1 LogMAR = 5 ETDRS letters
- IV. 15 ETDRS letters = 0.3 LogMAR
- V. A less positive/more negative LogMAR is an improvement of vision
- VI. An increase in the number of ETDRS letters read is an improvement of vision

On-Chart subjects: defined as being able to read at least 3 ETDRS letters on a single line on the ETDRS chart at either 4 or 1 meters

- a. Have an obtainable Snellen equivalent obtained directly from ETDRS chart
- b. Each Snellen equivalent is assigned a LogMAR value

Off-chart Subjects: defined as a subject who cannot read at least 3 ETDRS letters on a single line of the ETDRS chart at either 4 or 1 meters and thus have no Snellen equivalent obtainable from ETDRS chart

- c. These subjects are categorized as able to either count fingers (CF), detect hand motion (HM), detect light perception (LP) or are no-light perception (NLP)
- d. For those categorized as either CF or HM a method for deriving LogMAR visual acuity is pre-specified
- e. The distance at which CF/HM vision was obtained is recorded per the standard operating procedure
- f. Study database derives the LogMAR based on this distance and the finger/hand dimensions of the examiner, per pre-specified method.

Treatment-Emergent Adverse Events (TEAE)

Treatment-emergent adverse events (TEAEs) are defined as AEs that started after study treatment administration at Visit 3 or that represent an exacerbation of a condition that is present at baseline after treatment administration. Worsening of visual acuity determined by the investigator to be due to progression of LHON will not be considered as an AE. Any AE with an unknown start date will be considered treatment-emergent if the event does not stop prior to study treatment administration. AEs with partial dates are described in [Section 5.7.2](#).

Prior and Concomitant Treatment

Prior treatments will be defined as any treatments with start date and time prior to the study treatment administration date and time.

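### The subject-responder test counts a between-eye event but takes its expected rate under H0 from a different, single-eye event

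*SAP*

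**What the plan says.** SAP 5.6 (Subject Responder) counts "a subject whose ETDRS score of the treated eye is at least 15 letters better than the sham eye", or whose treated eye is at least 0.3 LogMAR better than the sham eye. The two limbs are the same margin on the SAP's own conversion, "15 ETDRS letters = 0.3 LogMAR". The additional subject criteria in SAP 5.6 are also between-eye; the first takes "a subject whose change of LogMAR from baseline in the treated eye is at least -0.2 better" than the sham eye's change, and two of the four use contrast sensitivity.

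SAP 5.6 (Eye Responder, Definition 1) is a single-eye event: a gain of at least 15 letters from baseline, or "being better than a Snellen acuity equivalent of 20/200".

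SAP 9.5.5 (Subject responders) plans, at Weeks 48, 72 and 96, "a randomization test comparing the observed rate of responders to the expected rate of responders under" H0, which it describes as absence of treatment effect. It then says: "Expected rate is defined as responder rate in the Sham group based on an improvement of at least 15 letters in the ETDRS score" compared with baseline, or acuity better than 20/200. That is the event of Eye Responder Definition 1. Eye responders have their own test, McNemar, in SAP 9.5.5 and Protocol 12.4.2. SAP 9.5.3 makes every analysis other than the primary one supportive.

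**The concern.** The rate being tested and the rate it is tested against describe different events. The first asks whether one eye beats its fellow by a margin. The second asks whether a sham eye improved or reached a threshold, with no reference to the fellow eye. If both eyes improve together, sham eyes respond often while the between-eye rate stays where it was. If both decline together, sham eyes rarely respond and the between-eye rate again does not move.

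The consequence depends on how the sham rate is used, which the SAP does not say:

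- **Reading (a):** the sham rate is a fixed null value. The test then does not hold its error rate in general, and the p-values can be wrong in either direction.
- **Reading (b):** the test swaps GS010 and sham labels within subject and recomputes the statistic each time. Error is then controlled, but the stated expected rate is not the null value.

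Under both readings, observed against expected can look like benefit or harm when there is none.

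**Working it through.** **Inputs from the documents.** Margin 0.3 LogMAR (SAP 5.6); n = 36 and an SD of 0.594 (SAP 3.3: "the between-eye difference in change from baseline was calculated as 0.594"); two-sided alpha 0.05. That SD is for a difference in change, whereas the main subject-responder definition uses acuity at the visit, so a range of SDs is shown. The documents give no sham eye-responder rate; 20% and 50% are assumptions.

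**The plan's own figure.** SAP 3.3 states 84% power for 0.3 LogMAR with SD 0.594 and n = 36. A paired t-test with noncentrality (0.3/0.594) × √36 = 3.03 gives 83.8%. The figure reproduces.

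**True null rate.** Let D be the GS010 eye minus the sham eye in LogMAR; lower is better. With no effect and a normal D with mean 0, the expected subject-responder rate is P(D ≤ −0.3) = Φ(−0.3/SD). This gives 15.9% for SD 0.3, 30.7% for SD 0.594 and 35.4% for SD 0.8. Mean acuity, and any change common to both eyes, do not enter.

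**Reading (a), sham rate fixed.** Exact two-sided binomial test, n = 36. At a null value of 20% it rejects in favour of GS010 at 13 or more responders. At 50% it rejects against GS010 at 11 or fewer.

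| SD of D | True null rate | Falsely favours GS010, null value 20% | Falsely rejects against GS010, null value 50% |
|---|---|---|---|
| 0.3 | 15.9% | 0.3% | 99% |
| 0.594 | 30.7% | 29% | 57% |
| 0.8 | 35.4% | 53% | 34% |

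With the matching null value of 30.7%, the SD 0.594 case rejects 1.2% of the time for GS010 and about 1.8% against it.

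**Reading (a), sham rate estimated from the same subjects.** This was simulated with no effect. Assumed: baseline LogMAR mean 1.0 to 1.5 and SD 0.5; mean change −0.2 to +0.35; SD of change 0.594 per eye; between-eye correlation 0.5 for both, so that the SD of the difference in change is 0.594; and a biased coin on better or worse eye treated, with probability 2/3 or 0.8. The acuity difference at the visit then has SD √(0.5² + 0.594²) = 0.776, and the null subject rate is Φ(−0.3/0.776) = 35%. The scenarios were chosen to span sham rates.

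| Subject rate | Sham eye rate | Total false rejection |
|---|---|---|
| 35% | 65% | 84% |
| 35% | 44% | 30% |
| 35.0% | 34.5% | 20% |
| 35% | 27% | 30% |
| 35% | 20% | 55% |

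The middle row isolates a second problem. The two rates almost agree, yet treating an estimated rate as fixed gives 20%. A plain binomial test against a known 34.5% gives 3.5%.

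**Reading (b), same assumptions.** The statistic is subject responders minus sham eye responders, recomputed at each re-randomization. Total false rejection is 2.7% to 4.1% when re-randomization follows the assumed minimization, and 1.85% to 2.65% with independent fair swaps. At a true 0.3 LogMAR effect, power is 54% to 61%, against 51% to 54% for the between-eye count alone. So the mismatch costs neither error control nor power here. What stays wrong is the stated expected rate: the subject rate is 35% with no effect, while sham eye rates run from 20% to 65%, a gap of +15 to −30 percentage points.

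**The case against.** Four points deserve an answer.

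- **A third reading.** The sentence on the test does not cite the subject-responder definition, and the only criterion it spells out is the single-eye one. Observed and expected could both be eye-level rates, GS010 against sham, and the null value would then be right. But the heading is Subject responders, SAP 5.6 defines that term separately, and eye responders already have a McNemar test. On this reading SAP 9.5.5 would still contradict SAP 5.6.
- **The named test is valid.** The large percentages belong to a fixed-null binomial test that the SAP does not name. This is fair: a randomization test taken literally controls error, and reading (b) confirms it. But such a test generates its own null, so the sentence defining the expected rate is then both unneeded and untrue, and two programmers could implement different tests.
- **The numbers are assumptions.** Sham rates, baseline values, correlations and coin probability are not in the documents, and 0.594 is an SD of change. They show that the error can be large in either direction, not how large it will be.
- **The reach is small.** This stands. The analysis is supportive, nothing visible says that the additional subject criteria go through this test, and the table shells are not available to show how the expected rate would be displayed.

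**Conclusion.** The concern holds. The expected rate in SAP 9.5.5 belongs to a different event from the one SAP 5.6 defines for subject responders, and nothing in the documents makes the two rates equal without a treatment effect. That conclusion needs no simulation.

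Size depends on the reading. With the sham rate as a fixed null value, illustrative one-direction false rejection runs from 0.3% to 99%, and the direction is unknown in advance, so the rule cannot be defended as conservative. With within-subject re-randomization, error is controlled and only the stated benchmark is wrong. These sizes assume normal differences, exchangeable eyes under no effect, 36 subjects and the sham rates shown.

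The primary analysis and the protocol's responder endpoint, tested by McNemar, are untouched. This should be fixed, but it does not threaten the trial's main conclusion.

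**What to change.** Delete the sentence that defines the expected rate from the sham eye-responder rate. State that the counted event is the between-eye subject responder of SAP 5.6, and that its distribution under H0 comes from re-randomizing GS010 and sham labels within subject. Re-randomization should follow the allocation actually used: SAP 3.4 says Efron's "minimization method will be used in the randomization process to balance as much as possible the two treatment groups" in the best-seeing eyes. Report the mean of that distribution as the expected rate. With independent fair swaps this mean is simply the number of subjects whose eyes differ by the margin in either direction, divided by 2n. Apply the same rule to the additional subject criteria if they are tested.

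A simpler alternative is an exact sign (McNemar) test of subjects whose GS010 eye is better by the margin against subjects whose sham eye is better by the same margin. Under independent fair allocation its size by enumeration is 2.4%, 2.9% and 3.0% for SD 0.3, 0.594 and 0.8. Under the assumed minimization it is only approximate and was conservative in simulation: size 1.1% to 2.3% and power 40% to 44%, about 10 points below the re-randomization test of the between-eye count.

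The cost is SAP wording and a small program change. There are no new data and no change to a protocol endpoint or to Eye Responder Definition 1. Re-randomization needs the allocation rule from the response system; the sign test does not. Protocol Appendix V bars SAP amendment once the code is broken, so the change must come before the Week 48 unmasking.

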### Eye responders

The responder analyses at both Week 48 , Week 72 and Week 96 will be based on a McNemar test comparing all-GS010 eyes against all-Sham eyes.

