12.2 Sample Size

Sample size calculation is based on the primary endpoint (LogMAR) and on the paired comparison of treated and sham eye. There is no published data regarding the within subject variance and the sample size calculation through paired comparison will therefore be very speculative for two reasons. The first reason is the within subject correlation between right and left eye and the second reason is the absence of information on the within and between subject variance of the LogMAR. Usually the within subject correlation is positive and the use of a null correlation is conservative. The absence of information on the LogMAR requires a second rough approximation of the mean and variance of LogMAR because the mean of ETDRS (Lam et al. 2014) is highly correlated to the variance of ETDRS ($R^2 = 0.839$ for the log-log relationship). This correlation is in favor of the use of the LogMAR to stabilize the variance but the transformation from ETDRS mean and variance to LogMAR mean and variance requires additional assumptions. Starting with a mean 23.4 and a standard deviation of 28.3 (Lam et al. 2014) and a difference of 20 letters on average between treated and sham eye, using the relationship between the log mean and the log variance obtained with Lam et al. (2014) results (log variance = 1.743 log mean + 0.48, $R^2 = 0.839$) and assuming a perfect lognormal distribution of ETDRS, the difference in means of the lognormal distributions is 0.65 (3.32 - 2.67) and the pooled standard deviation of the log distributions is 0.914. Assuming no correlation between both eyes, the within subject standard deviation is $(2x0.914^2)^{0.5} = 1.29$. The standardized difference in means is therefore 0.65/1.29 = 0.504 rounded to 0.50. The sample size required to get a power of 85% is exactly 36 subjects.

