12.4.2 Secondary Analysis

The treatment estimate at Week 96 will be based on the same statistical approach as the primary endpoint analysis. Another analysis will compare time course of the response up to Week 96 using the mixed model procedure. The responder analyses at both Week 48 and Week 96 will be based on a McNemar test for paired samples. To verify whether the treatment effect is dependent upon the better-seeing eye or the worse-seeing eye at study entry, a test of homogeneity of subgroups (better-seeing or worse-seeing eye treated) effects in stratified paired binary data (Zhao 2014) will be performed.

Like the primary endpoint, a meta-analysis will be performed combining both studies (GS-LHON-CLIN-03A (RESCUE) and study GS-LHON-CLIN-03B (REVERSE). A conditional logistic model will be used to assess the effect of better- and worse-seeing eye at study entry and the effect of time from onset of disease and the effect of treatment.

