#### Primary Analysis for EMA

The null and alternative hypotheses for the primary endpoint are defined below

$$H_0: \mu_{\text{All-GS010}} = \mu_{\text{All-Sham}}$$

$$H_1: \mu_{\text{All-GS010}} \neq \mu_{\text{All-Sham}}$$

Where  $\mu$  presents the mean change from baseline to Week 48 in LogMAR. “All” represents all eyes treated with GS010 or Sham

The primary analysis will be performed on the ITT population. The change from baseline to Week 48 in the LogMAR acuity will be the primary response. The change from baseline of all-GS010 eyes will be compared to the change from baseline of all-Sham eyes (intra-subject comparison) using a mixed model of analysis of covariance (ANCOVA) using the following terms (or covariate) in the model:

- Subject as random factor
- Eyes of the subject as random factor,
- Treatment and the
- Baseline LogMAR for each eye.

The analysis will be performed based on alpha of 0.05. The statistical significance in favor of GS010 against sham will provide evidence of the advantage of using GS010 for halting visual acuity loss or improving visual acuity in subjects with LHON with duration of vision loss of 6 months or less. The difference in the mean change from baseline (adjusted mean difference) to Week 48 between the two treatment groups and associated 95% confidence interval will be reported.

The center will not be included in the analysis as the number of subjects recruited per site will be very small. However, stratification by geographical area will be performed as a sensitivity analysis. Neighboring countries can be pooled together to reach at least 9 subjects per geographical entity. The pooling will be performed during the masked review of data.

All the model diagnostics will be checked.

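### The eye-responder McNemar test ignores best/worst eye status, the factor the minimisation balances; if the two eyes have different responder rates the test is conservative and loses power, by an amount the documents do not let one fix

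*SAP*

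**What the plan says.** **Test.** SAP 9.5.5 (Eye responders), for Weeks 48, 72 and 96, states that the analysis "will be based on a McNemar test comparing all-GS010 eyes against all-Sham eyes". Protocol 12.4.2 reads: "The responder analyses at both Week 48 and Week 96 will be based on a McNemar test for paired samples". Neither text has an eye-status term, and neither says whether the asymptotic or the exact version is meant.

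**Allocation.** Under SAP 3.4 "each subject will receive GS010 in one eye and sham treatment in the fellow eye", and Efron's minimisation is "used in the randomization process to balance as much as possible the two treatment groups (GS010 and sham) in the best-seeing eyes". Protocol 8.6 agrees. With 36 subjects this means close to 18 subjects treated in the best eye and 18 in the worst.

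**Endpoint.** The eye responder (Protocol 3.2; SAP 5.6, Definition 1) needs a gain of at least 15 letters or an acuity better than 20/200. SAP Definition 2 is an absolute threshold only, 20 letters or more. Early discontinuations count as non-responders.

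**Eye status elsewhere.** Protocol 4.1 calls it a possible confounder, and SAP 4.3 lists it among possible prognostic factors. It enters the LogMAR repeated-measures model and one sensitivity analysis of the EMA primary model. For responders, Protocol 12.4.2 plans a homogeneity test by eye treated and a conditional logistic model pooled with REVERSE.

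**The concern.** McNemar's null gives every discordant pair an independent 50:50 chance of favouring GS010. Some pairs will be discordant only because the best and worst eyes differ at entry. Which way such a pair points depends on which eye drew GS010, and the minimisation holds that split near even. These pairs therefore largely cancel by design, yet McNemar still counts them as noise. The structure is that of a two-period binary crossover analysed without the period, with eye status as the period.

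A gap in responder rates is plausible under the named endpoint by two routes. A best eye already better than 20/200 at baseline responds by staying there, whatever it received. The rate of 15-letter gains may also differ between the eyes. Subjects with vision loss in only one eye are eligible (Protocol 5.2.1), which makes the first route realistic.

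At stake is a stated secondary objective, whether the responder rate depends on treatment. With 36 subjects, a real effect could be missed although the allocation had already secured the power to see it.

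**Working it through.** **1. The plan's own figure.** The only sample-size statement concerns the primary paired comparison: "The sample size required to get a power of 85% is exactly 36 subjects", with standardised difference "0.65/1.29 = 0.504 rounded to 0.50". Check: n = ((1.960 + 1.036)/0.50)² = 35.9, so 36. Power at 36 is 85.1% by the normal formula and 83.1% by the noncentral t. The figure reproduces but says nothing about responders, for which no rate, discordance or power is given.

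**2. Formula.** Let pB = P(only the best eye responds) and pW = P(only the worst eye responds), with no treatment effect. Then pB − pW is the gap between the two eyes' responder rates. Score d = best response minus worst response (−1, 0, +1). With 18 subjects treated in each eye, McNemar's numerator is the sum of d over best-eye-treated subjects minus the sum over the others. Its variance is 36[(pB + pW) − (pB − pW)²]. McNemar uses 36(pB + pW). Hence

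r = true/assumed variance = 1 − (pB − pW)²/(pB + pW), and true size ≈ 2Φ(−1.96/√r).

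**3. Size** at nominal 5%, two-sided ("The analysis will be performed based on alpha of 0.05" is stated for the primary analysis and assumed here), 18/18 split:

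| pB | pW | gap | r | formula | enumerated, asymptotic | enumerated, exact |
|---|---|---|---|---|---|---|
| .20 | .20 | 0 | 1.00 | 5.0% | 4.7% | 2.7% |
| .30 | .10 | .20 | .90 | 3.9% | 3.6% | 2.0% |
| .40 | .05 | .35 | .73 | 2.2% | 2.2% | 1.1% |
| .30 | 0 | .30 | .70 | 1.9% | 1.7% | 0.7% |
| .42 | 0 | .42 | .58 | 1.0% | 1.0% | 0.4% |
| .50 | 0 | .50 | .50 | 0.6% | 0.7% | 0.3% |

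The gap alone does not fix the size. For a given gap it is lowest when no subject responds in the worst eye only (pW = 0).

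**4. Cause.** At best/worst rates .50/.05, asymptotic McNemar has size 4.7% under simple randomisation and 1.3% under Efron's coin (2/3 assumed). The balancing produces the shortfall.

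**5. Power, asymptotic tests.** 36 subjects, 2/3 coin, latent between-eye correlation 0.3 to 0.6, GS010 adding 25 points in each eye, 20,000 trials per scenario. The comparator is a Prescott-type test of d between best-eye-treated and worst-eye-treated subjects. Loss is the difference between matching ends of the ranges.

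| Sham best/worst | gap | McNemar size | McNemar power | Prescott-type power | loss (points) |
|---|---|---|---|---|---|
| .30/.30 | 0 | 4.3% | 65–77% | 65–77% | 0 |
| .50/.20 | .3 | 2.7–3.2% | 60–68% | 68–78% | 8–10 |
| .60/.20 | .4 | 1.9–2.2% | 56–62% | 71–79% | 15–17 |
| .70/.20 | .5 | 1.2–1.3% | 51–56% | 77–83% | 26–27 |
| .70/.10 | .6 | 0.6–0.7% | 46–49% | 83–88% | 37–39 |

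A separate 18/18 run at .50/.05 (gap .45), rising to .80/.30 on GS010, gave 67% v 87%, a loss of 20.

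**6. Power, exact against exact.** Exact McNemar v exact re-randomisation, 18/18, correlation 0.5:

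| Sham best/worst | GS010 best/worst | gap | exact McNemar | exact re-randomisation |
|---|---|---|---|---|
| .17/.17 | .40/.40 | 0 | 61% | 61% |
| .30/.10 | .55/.30 | .2 | 51% | 57% |
| .40/.10 | .70/.35 | .3 | 66% | 76% |
| .50/.10 | .80/.35 | .4 | 58% | 78% |
| .50/.05 | .80/.30 | .45 | 55% | 80% |

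**7. Scenario from the protocol's own distribution.** Lognormal letters (log means 2.67 and 3.32, SD 0.914, Protocol 12.2), 20/200 taken as 35 letters (assumed), best eye always the higher under sham. Size is 1.9–2.6% asymptotic and 0.8% exact. Power of exact McNemar v exact re-randomisation is 49% v 67% at zero eye correlation and 64% v 73% at 0.5, losses of 18 and 9 points.

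**The case against.** The strongest reply is that McNemar is a valid paired test whose error here is in the safe direction, on an analysis that SAP 9.5.3 treats as supportive and for which the trial was not powered. Protocol and SAP agree on it. All of that stands. It limits the weight of the point but leaves the mechanism untouched.

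The gap itself is unknown. The absolute limb favours the best eye, but the gain limb may leave the worst eye more room to qualify, so the two may partly offset. The protocol also describes the second eye following the first after a median of two months, so a gap at entry may narrow by Week 48. This also stands, and it is why the loss can only be given as a range.

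A reader might infer that a good eye losing vision, beside a first-affected eye with little left to lose, drives the problem. Under the named endpoint it does not. If the good eye falls past 20/200 and the other stays poor, both are non-responders, the pair is concordant and McNemar drops it. That picture gives discordance only under the SAP's additional loss-based criteria (eye Criteria 1 and 2).

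It can be said that eye status is already handled. It is not overlooked, but the homogeneity test concerns interaction and the logistic model belongs to the pooled analysis. Neither changes the reference distribution of the within-trial McNemar test.

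The comparator is not perfect either. With a normal cut-off the Prescott-type test can reach about 6% in extreme cases, although it held 4.6–5.5% in the scenarios of step 5. The exact 18/18 re-randomisation test is itself discrete, with size 2.0–2.9%. Set against asymptotic McNemar it loses about 10 points at no gap (71% v 61%) and breaks even near a gap of 0.25 (69% v 69%). The statement that nothing is lost at equal rates holds like with like.

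**Conclusion.** The point holds as a conditional loss of efficiency in a secondary analysis. The planned test ignores the factor that the allocation balances, so it is conservative whenever best and worst eyes have different responder rates.

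For the asymptotic test there is no loss at equal rates. At a gap of 0.2 to 0.3 the size is about 3% and the loss about 5 to 10 points. At 0.4 they are about 2% and 15 to 17 points. At about 0.45 to 0.5 or more they are about 1% and 20 points or more. In the limiting case of no worst-only responders, size is lower at the same gap and 1% is reached at 0.42. Exact against exact, the loss was already 20 points in the 0.4 scenario. Part of exact McNemar's low size is discreteness, present without any gap.

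A reader might take 1% size and a 20-point loss as what to expect. The documents do not support that: they give no responder rates, and the scenario built on the protocol's own distribution lost 9 to 18 points. Nor do they support a claim of inflated type I error. The responder rates, coin probability, eye correlation and the 35-letter equivalence are all assumptions.

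**What to change.** Before unmasking, make the main eye-responder test one that accounts for eye status:

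- Score each subject as best-eye response minus worst-eye response, and compare best-eye-treated with worst-eye-treated subjects.
- Use a Prescott-type test, or preferably take the p-value from re-randomisation under the actual minimisation, because the normal cut-off can run slightly above 5% in extreme cases. State which is used. Re-randomising under the real biased coin should be less discrete than the fixed 18/18 version in step 6, since other splits can occur.
- Report the average of the two groups' paired risk differences (GS010 minus sham) with its 95% CI.
- Keep McNemar as a supplementary row, stating whether it is exact or asymptotic.

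The Mainland-Gart variant is a poor main choice: it drops ties and has little information when nearly all discordant pairs favour the best eye.

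Cost: no new data, since eye status is fixed before randomisation, and a short piece of code. The SAP already uses a randomisation test for subject responders, so the approach is not foreign to the plan. The minimisation parameters, which the documents do not give, must come from the randomisation vendor. Changing Protocol 12.4.2 as well is an amendment under Protocol Section 15. Protocol Appendix V bars SAP amendments once the code is broken and treats later additions as ad hoc, so the change must come first.
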